9.2. Recording and Reporting AEs and SAEs

For each SAE the following information will be collected:

Feasibility of ambulatory pleurodesis
Protocol V2
IRAS: 330188
CI: [name]
26/06/2023

- Full details in medical terms and case description
 - Event duration (start and end dates, if applicable)
 - Action taken
 - Outcome
 - Seriousness criteria
 - Causality in the opinion of the investigator
 - Whether the event is considered expected or unexpected.

Any change of condition or other follow-up information should be faxed to the [Sponsor/GCTU] as soon as it is available or at least within 24 hours of the information becoming available. Events will be followed up until the event has resolved or a final outcome has been reached.

9.3. Recording and Reporting USARs

All USARs occurring from the intervention until 6 months post termination of trial treatment must be reported to the NHS REC. The Sponsor will perform this reporting. The assessment of expectedness will be performed by the PI against the known information for the trial. USARs must be reported no later than 15 calendar days after the Sponsor has first knowledge of the event. Any relevant follow-up information should be sought and reported as soon as possible after the initial report. As soon as a site suspects that a SAR may be a USAR they must contact the CI, sponsor representative and the trial manager immediately. The reporting timeframe starts at day 0 when the Sponsor is in receipt of a minimum set of information:

- Sponsor trial reference and trial name
- Patient trial number and date of birth
- Date of notification of the event
- Medical description of the event
- Date and time of the onset of the event (including event end date if applicable)
- Causality assessment
- Seriousness of the event, particularly if life threatening or fatal
- An identifiable reporter (e.g., Principal Investigator)

This information must be provided on USAR report form. The site is expected to fully cooperate with the Sponsor in order that a full and detailed report can be submitted to the NHS REC within the required timelines.

PIs will be informed of all USARs by the Sponsor and CI.

Feasibility of ambulatory pleurodesis
Protocol V2
IRAS: 330188
CI: [name]
26/06/2023

Responsibilities

Principal Investigator

- Checking for AEs and ARs when participants attend for treatment or follow up
- Using medical judgement in assigning seriousness and causality and providing an opinion on expectedness of events.
- Ensuring that all SAEs and SARs, including USARs, are recorded and reported to the Sponsor within 24 hours of becoming aware of the event and provide further follow-up information as soon as available.
- Ensuring that AEs and ARs are recorded and reported to the Sponsor in line with the requirements of the protocol.

Chief Investigator

- Clinical oversight of the safety of trial participants, including an ongoing review of the risk/benefit.
- Using medical judgement in assigning seriousness, causality and expectedness of SAEs where it has not been possible to obtain local medical assessment.
- Using medical judgement in assigning expectedness to SARs.
- Immediate review of all USARs.
- Review of specific SAEs and SARs in accordance with the trial risk assessment and protocol.

Sponsor

- Assessment of expectedness of any USARs
- Expedited reporting of USARs to the REC within required timelines
- Notification of all investigator sites of any USAR that occurs

9.6. Reporting Urgent Safety Measures

An Urgent Safety Measure (USM) is an action that the Sponsor or an Investigator may take in order to protect the subjects of a trial against any immediate hazard to their health or safety. Upon implementation of an USM by an Investigator, the Sponsor must be notified immediately and details of the USM given. The Sponsor must inform the NHS REC within 3 days of the USM taking place in accordance with the Sponsor's standard operating procedures.

Feasibility of ambulatory pleurodesis
Protocol V2
IRAS: 330188
CI: [name]
26/06/2023

10. TRIAL MANAGEMENT AND OVERSIGHT

The monitoring team employs a risk-based approach to monitoring. This approach focuses efforts on the most crucial data and process elements to allow for more efficient monitoring practices while maintaining the quality of the overall study conduct.

The team will employ remote monitoring of clinical trial with a focus on safety, study endpoints, data completion and data outliers. Source documentation, including study logs, Informed Consent Log, Protocol Violation/Deviation Log and the Serious Adverse Event Report log will be monitored to ensure that the sites are adhering to the study protocol and procedures.

In collaboration with the data management team, the monitor will create and utilize reports outlining data totality and timeliness, missing values to generate queries and optimize reconciliation of data.

Clinical sites will maintain copies of all source documents, which may be either paper or electronic, at each site. The monitors will review the source documents to determine whether the data reported is complete and accurate. They will also verify that all adverse events exist on the source documents, are consistent with the protocol, and are documented in the appropriate format.

Source documents include medical charts, initial hospital admission reports, operative procedure records, discharge and re-admission reports, consult notes and other study-related notes. At an on-site visit, the study monitors reserve the right to copy de-identified records in support of all adverse events and outcomes.

The monitors will also confirm that the regulatory binder is complete and that all associated documents are up to date. The regulatory binder should include but is not limited to all revisions of the protocol and informed consent, approvals for all of the above documents, and correspondence; investigator's agreement and agreement amendments; DOA log; CVs and appropriate training certificates of all study personnel and monitor site visit log.

If problems are identified during the monitoring visit missing study documents, etc., the monitor will assist the site in resolving the issues.

11. WITHDRAWAL OF PATIENTS FROM THE TRIAL

Participants are free to withdraw from the trial at any point and return to standard care. This can be done by contacting the trial team in writing, telephone or in person. Patient information up to that point would be included with patient consent. We would also seek to record the reasons for their withdrawal with their consent.

Feasibility of ambulatory pleurodesis
Protocol V2
IRAS: 330188
CI: [name]
26/06/2023

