Feasibility of ambulatory pleurodesis
Protocol V2
IRAS: 330188
CI: [name]
26/06/2023

PROTOCOL

Study Title:	Feasibility of ambulatory pleurodesis
Chief Investigator:	[name]
Sponsor:	TVRA
Funder:	TVRA

Feasibility of ambulatory pleurodesis
Protocol V2
IRAS: 330188
CI: [name]
26/06/2023

TABLE OF CONTENTS:

- 1. Study Summary**
- 2. Trial Background**
- 3. Objectives and Study End Points**
 - Primary Objective
 - Secondary Objectives
 - Primary Outcome Measure
 - Secondary Outcome Measures
- 4. Overview of study pathway**
- 5. Selection of Patients**
 - Inclusion Criteria
 - Exclusion Criteria
 - Screening and Informed Consent
 - Screening Logs
- 6. Study Procedures**
- 7. Data Collection**
 - Case Report Form
- 8. Data Management & Confidentiality**
 - Confidentiality
 - Missing Data and Data Queries
- 9. Safety Reporting**
 - Definitions of Adverse Events
 - Reporting Procedures
- 10. Trial Management & Sponsor Oversight**
 - Trial Management Group
 - Sponsorship and Monitoring Arrangements
- 11. Withdrawal of Patients from Trial**
 - Handling withdrawal requests
 - Use of data following withdrawal
- 12. Trial Funding**
- 13. Publication and Dissemination Plans**
- 14. References & Bibliography**

Feasibility of ambulatory pleurodesis
 Protocol V2
 IRAS: 330188
 CI: [name]
 26/06/2023

1. STUDY SUMMARY:

Overall Aim:	Is the study protocol deliverable?
Primary Objective:	
 Can patients with malignant pleural effusions undergo chest drainage and talc. Pleurodesis on an ambulatory basis
Secondary Objective	
 What are the patient perspectives of this protocol?
Target Accrual:	10 patients
Inclusion & Exclusion Criteria:	
Inclusion
 
 Malignant pleural effusion Life expectancy >30 days WHO PS 1-2 (3 if due to exertional dyspnoea) 
Exclusion
 
 Previous failed pleurodesis Known non-expansile lung

Feasibility of ambulatory pleurodesis
Protocol V2
IRAS: 330188
CI: [name]
26/06/2023

	
 • Pregnancy • Age <18
Data Collection Summary:	•
Anticipated Duration of Recruitment	12 months
Duration of Patient Follow-up	30 days
Definition of End of Trial	Drain removal and completion of d+30 questionnaire

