- After this we would open the drain again and drain up to 500mls and close the drain for an hour.
- We would repeat this as required and again the patient would return home with an ambulatory bag left open.
- If the effusion has resolved but the lung has not fully expanded due to underlying disease then we would simply remove the chest drain as pleurodesis will not be possible.

On day 3:

- The drain would be flushed, aspirated and the output assessed.
- If there is still fluid output we would drain up to 500mls and close the drain for an hour and repeat.
- If there is no further output we would arrange a chest x ray to ensure the effusion has resolved.

Feasibility of ambulatory pleurodesis
Protocol V2
IRAS: 330188
CI: [name]
26/06/2023

- We would then remove the drain and repeat the x-ray to confirm there have been no complications.
- We would then consider the intervention complete and revert to standard care

If there was still significant fluid output we would repeatedly drain 500ml volumes of fluid and clamp the drain for an hour after each 500ml until dry.

We would ask patients to complete a very brief questionnaire (visual analogue scale) on breathlessness and chest pain on day 1 - before intervention, 1 hour post drain insertion, at the end of the day and on day 2 and 3 on first encounter and at the end of the day. We would also repeat the questionnaire on day 30 along with their satisfaction with the protocol.

DAY 1	DAY 2	DAY 3	DAY 4
Seldinger 16Fg drain inserted	Assess output - aspirate and flush drain. Proceed to D3 if no out put.	Assess output - aspirate and flush drain. Repeat Day 2 protocol if required	Assess output: if >240mls / 24 hours repeat Day 2 protocol
Thoracocentesis – up to 1000mls or patient tolerance	Thoracocentesis – up to 500mls or patient tolerance	CXR to confirm >75% pleural apposition	Seldinger drain removed
Clamp for 1 hour	Clamp for 1 hour	Instil 4g steritalic with 3mg/kg Lidocaine and 50ml 0.9% NaCL flush	CXR to confirm >75% pleural apposition
Thoracocentesis – up to 500mls or patient tolerance	Thoracocentesis – up to 500mls or patient tolerance	Clamp for 2 hour	
Repeat as able	Repeat as able	Connect to ambulatory bag and leave 'open'	
Connect to ambulatory bag and leave 'open'	Connect to ambulatory bag and leave 'open'		

5. SELECTION OF PATIENTS:

Inclusion criteria:

- Malignant pleural effusion
- Life expectancy >30 days
- WHO PS 0-2 (3 if due to exertional dyspnoea)

Patient exclusion criteria:

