6. STUDY PROCEDURES

Study protocol outlined above. Additionally, we will collect Patient related outcome measures relating to breathlessness and pain each day and at day +30. We will also seek patient feedback on the protocol at this point.

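### Section 11 gives a patient who chooses to leave the ambulatory pathway no way to stay in follow-up, so the day 30 views of those who rejected it tend to be lost

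*Protocol*

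**What the plan says.** Section 11 of the protocol sets one route for a patient who wishes to leave: "Participants are free to withdraw from the trial at any point and return to standard care". On data it says "Patient information up to that point would be included with patient consent", and on motive "We would also seek to record the reasons for their withdrawal with their consent". It does not mention anything that happens afterwards. The table of contents lists a subsection titled "Use of data following withdrawal", but the body of Section 11 has no text under that title.

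Patient perspective is the secondary objective (Sections 1 and 3). Section 4 schedules visual analogue scales for breathlessness and chest pain on days 1 to 3 and again at day 30, and asks about satisfaction at day 30 only. Section 6 confirms the timing: "We will also seek patient feedback on the protocol at this point". Section 7 has the trial team run the day 30 survey by telephone or face to face. The analysis stated beside the sample size of 10 is a thematic analysis of the feedback.

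On safety, Section 9.2 says "Events will be followed up until the event has resolved or a final outcome has been reached", and Section 9.3 says "All USARs occurring from the intervention until 6 months post termination of trial treatment must be reported to the NHS REC". Neither mentions patients who have withdrawn.

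**The concern.** Two different decisions share one exit. A patient may want to stop the ambulatory pathway, for instance because going home with a drain is unacceptable, and still be willing to answer questions. Another may want no further contact. Section 11 offers both the same step and provides only for information gathered before it.

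This matters here because the pathway is the intervention, standard care is the alternative offered at enrolment (Section 4), and the study asks whether patients find the pathway acceptable. A patient who prefers standard care part-way through is among the most informative on that question. If that patient is handled under Section 11 and no day 30 contact follows, the feedback comes mainly from those who stayed. The loss is selective, and a thematic analysis of the remaining answers cannot reveal it.

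There is a second, smaller gap. For a patient who leaves because of an adverse event, site staff are not told whether, or on what consent, the follow-up in Sections 9.2 and 9.3 goes on.

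The point concerns data after the patient leaves. Whether withdrawn patients count in the primary feasibility result is a separate question.

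**Working it through.** The protocol has no figure of its own to reproduce: 10 is stated without derivation, and there is no withdrawal rate or dropout allowance. The check is mainly a comparison of passages.

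**1. Ways off the pathway, and what follows each.**

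| Situation | Where | Called withdrawal? | Day 30 contact |
|---|---|---|---|
| Intervention completed: "We would then consider the intervention complete and revert to standard care" | Section 4, day 3 | No | Yes, as scheduled |
| Lung does not expand, drain removed | Section 4, day 2 | No | Nothing exempts the patient |
| Patient chooses to leave | Section 11 | Yes, the only route described | Not provided for; data rule looks back only |

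The first two rows show that the protocol can take a patient off the pathway without ending participation. The third row has no equivalent arrangement.

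**2. What is lost in the third row.** Satisfaction is scheduled once, at day 30. A patient who leaves on day 1 or 2 keeps the earlier scale scores, with consent. Under the natural reading, the patient loses the remaining early scores, the day 30 scores and the only scheduled satisfaction answer.

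**3. Section 11 against Sections 9.2 and 9.3.** Section 11 governs use of a withdrawn patient's information. Section 9.2 governs how long events are followed. Section 9.3 governs sponsor reporting until 6 months after treatment. All three can be applied together if safety follow-up continues after withdrawal. No passage says that it does, so this is an unreconciled gap and not a conflict.

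**4. Size, as an illustration only.** Let n = 10 be enrolled, m have no day 30 answer, and x of the remaining 10 − m give a particular answer. The proportion in all 10 lies between x/10 (none of the missing would give it) and (x + m)/10 (all would). The width is m/10 whatever x is. The values of m are assumed.

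| m (assumed) | Patients supplying day 30 feedback | Width of possible range |
|---|---|---|
| 1 | 9 | 1/10 = 10 points |
| 2 | 8 | 2/10 = 20 points |
| 3 | 7 | 3/10 = 30 points |

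**The case against.** The best case for the protocol is that Section 11 describes a right exercised by the patient and does not define every departure from the pathway as leaving the trial. Several stronger readings are tempting, and the text does not support them.

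- **That all leaving of the pathway is leaving the trial.** Section 4 shows completion and non-expansion of the lung taking patients off the pathway without withdrawal. The point holds only for patients handled under Section 11.
- **That later data collection is forbidden.** Section 11 says what is included; it does not prohibit more. That collection stops is the natural reading, but it is an inference.
- **That Section 11 contradicts Section 9.2.** The two have different subjects and can stand together.
- **That a hospital admission prompting the exit goes unrecorded.** Section 9 counts inpatient hospitalisation as a serious adverse event, to be reported to the sponsor within 24 hours, with its outcome collected. An admission before withdrawal is captured.
- **That satisfaction will be overstated by a known amount.** No satisfaction proportion is planned, and any figure depends on assumed inputs. Suppose 7 of 10 are satisfied and 2 are lost: the observed value is 7/8 = 87.5% if both were dissatisfied, but 5/8 = 62.5% if both were satisfied.

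It is also fair to say that Section 11 seeks the reason for withdrawal, which gives some access to the views of those who leave. That stands as partial mitigation. It depends on consent and does not replace the day 30 scores and satisfaction contact. Consent material, which is not available here, may distinguish levels of withdrawal; if so, the protocol should match it.

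None of this supplies what is missing: a stated option for the patient who leaves the pathway by choice but would still take part at day 30.

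**Conclusion.** The concern holds in a limited form. Section 11 gives a patient who chooses to leave one route and a data rule that looks only backwards, so the patient-perspective objective tends to lose the people whose views bear most directly on acceptability. The conclusion rests on two assumptions: that Section 11 is applied as it naturally reads, and that patients who choose to leave are more often dissatisfied than those who stay. The second is plausible, but the protocol gives no evidence for it.

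The size cannot be estimated from the document. The most that can be said is the 10-point widening per missing answer, as a bound on any day 30 proportion and not as a bias. The safety element is a lack of reconciliation only.

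The change is worth making before recruitment: it decides whom the trial contacts, which a later analysis plan cannot restore. It does not put the primary objective in doubt.

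**What to change.** Split Section 11 in two.

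- **(a) Stopping the ambulatory pathway.** The patient stays in the study, if they agree, for the day 30 scales and feedback contact and for safety follow-up.
- **(b) Withdrawing from further data collection.** This needs an explicit request from the patient.

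For each, state which safety follow-up under Sections 9.2 and 9.3 continues, in terms consistent with the consent form. This would also supply the content that the table of contents announces. In the thematic analysis, identify whether each piece of feedback came from a patient who completed the pathway or from one who stopped early.

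The cost is a short amendment with matching consent wording, and a brief call to a few patients who left the pathway. The day 30 contact is already planned, so no new procedure is needed, and clinical management does not change. Some who left may not welcome the call; making (a) conditional on agreement deals with that.

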12. TRIAL FUNDING

There is no specific funding sought for this trial due to the small sample size.

